5.6.2 SARS-CoV-2 Rapid Antigen Test Results

State or local health department regulations may require reporting of incident cases of SARS-CoV-2 infection. The Investigator will be responsible for contacting state or local SARS-CoV-2 surveillance coordinators to ensure study procedures comply with all reporting requirements.

Participants will be informed that:

- Results are not meant to replace recommended clinical and/or occupational molecular tests;
- False positive and false negative results are possible;
- Receiving a negative diagnostic result should not alter their preventive behaviors, given that
 results are specific to the date and time they are collected, and current assays may not be
 sensitive to all infections;
- Results will not be shared with the participants' medical providers.
- Participants should consult their personal medical provider if they have questions, concerns, or any medical needs related to their illness;
- They should follow their employer's guidelines for reporting illnesses and returning to work.

6. Statistical Considerations

This randomized, three arm, active comparator trial will compare the clinical efficacy of NVX 2023-2024 updated vaccine (Arm 1) with a single dose of the mRNA 2023-2024 updated strain (Arm 2) as well as non-boosted comparison group (Arm 3). The study hypotheses are 1) to compare vaccine efficacy (VE) between participants who receive either the NVX (Arm 1) or mRNA 2023-2024 updated strain (Arm 2) with the non-boosted participants who are recommended to be boosted based on CDC, state or organizational guidelines but decline the 2023-2024 updated vaccine and 2) to determine the relative vaccine efficacy (relative VE) of the Pfizer mRNA 2023-2024 updated vaccine and the NVX 2023-2024 updated vaccine in preventing SARS-CoV-2 infection to confirm non-inferiority for NVX. Detailed plans for statistical analysis are provided in Appendix S1. Statistical Analysis Plan (SAP) and Appendix S2. Post-Vaccination SAP. These plans have been updated to reflect revised power calculations based on more accurate estimations of assumed rates of infection throughout the study period. As a result of these revised power calculations, the surveillance period has been expanded from 20 to 24 weeks to ensure sufficient data capture within the study.

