6.1 Sample size & Power Considerations

6.1.1 Sample Size for Primary Objectives

Power and sample size are examined for both primary objectives to 1) compare VE between vaccinated arms (both NVX and mRNA) and the non-vaccinated comparison arm with a 2-sided alpha=0.05 superiority test and 2) determine non-inferiority of NVX 2023-2024 formula vaccine variant compared to a single dose of Pfizer mRNA 2023-2024 updated vaccine with a 1-sided alpha=0.05 confidence interval. The rate of CLI-associated SARS-CoV-2 infection, confirmed by COVID-19 rapid antigen test (RAT) in those not vaccinated with the 2023-2024 formulation is expected to be 60 per 100,000 person-days. We expect those choosing not to vaccinate in Fall 2023 to Spring 2024 to be a mix of unvaccinated and fully vaccinated but not boosted individuals, but to be conservative we will assume this group is solely comprised of fully vaccinated individuals. Using publicly available data on the historic case rates in Utah for COVID-19 from the week of November 20, 2022 to the week of July 30, 2023, 39 the average rate of cases in those fully vaccinated in Fall 2022-Spring 2023 is 39.64 per 100,000 person-days for those fully

vaccinated. From a survey conducted in spring of 2022, it has previously been reported that of those testing for COVID-19 44.2% report testing at a lab or clinic and 25.7% reported testing at a drive-thru clinic⁴⁰. Therefore, using at-home test kits to identify cases, we expect rates to be 43.1% higher (1/(0.257+0.442)) than what is shown on Utah's dashboard. This under-reporting adjustment to Utah's observed rates from last fall leads to a conservative estimate for the rate of CLI-associated SARS-CoV-2 infection, confirmed by COVID-19 rapid antigen test (RAT), in those not vaccinated with the 2023-2024 formulation to be 60 per 100,000 person-days. Using the same logic applied to the reports for those with a bivalent booster last fall, after adjusting for under-reporting, we estimate the infection rate to be 48 per 100,000 person-days in those vaccinated in Fall 2023 to Spring 2024.

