For the non-inferiority test in the second primary objective, the null hypothesis that the NVX vaccine of 2023-2024 formulation is inferior to the Pfizer vaccine of the 2023-2024 formulation is tested against the alternative that NVX is non-inferior. That is, H_0 : $rVE < 0 + \delta$ is tested against H_a : $rVE \ge 0 + \delta$, where δ is the "interval of equivalence", the range in which the effectiveness of the two vaccines would be considered clinically equivalent. Relative VE, or rVE, is calculated as 1- hazard ratio, HR, comparing

those receiving the NVX 2023-2024 formulation to those receiving the Pfizer 2023-2024 formulation, times 100, or 100*(1-HR). We believe an interval of -50% would be clinically acceptable. For example, if Pfizer reduces the hazard of infection by half, reducing the hazard by 25% (VE of 25%) would correspond to an rVE of -50%. Similarly, if Pfizer shows 80% VE compared to the non-vaccinated, a NVX VE of 70% would correspond to an rVE of -50%. For the power calculations for the second primary objective, the significance level is α =0.05.

Table 5 gives the power for testing the non-inferiority hypothesis with a sample of 600 enrolled patients per arm with an equivalence interval of -50%, with observed rVE ranging from -20 to 20 and observed rates of CLI-associated SARS-CoV-2 infection, confirmed by COVID-19 rapid antigen test (RAT) in the Pfizer arm ranging from 50 to 90 per 100,000 person-days. Additionally, an attrition rate of 15% from 600 is assumed. The power decreases as the observed case-rate in the Pfizer arm decreases or as the observed rVE decreases. Calculations were made in PASS 2023 using Non-Inferiority Tests for Vaccine Efficacy using the Hazard Ratio (Cox's Proportional Hazards Model). If we assume an infection rate of 60 per 100,000 person-days in the Pfizer vaccinated arm we have 81.12% power to determine non-inferiority of NVX for observed rVEs of 10 or greater.

Table 5. Power assuming 600 at enrollment for each group (NVX and Pfizer) accounting for 15% attrition for non-inferiority of NVX vs. Pfizer 2023-2024 formulations and a non-inferiority limit of -50 rVE.

Assumed rate of COVID-19 infection in 100,000 person days for Pfizer 2023-2024			Possible C	bserved Re	elative VE		
formulation arm	20	10	5	0	-5	-10	-20
50	86.88	74.60	67.13	59.16	51.02	43.03	28.63
60	91.71	81.12	74.00	65.94	57.33	48.57	32.20
70	94.84	86.12	79.58	71.75	62.97	53.70	35.66
80	96.84	89.88	84.08	76.70	67.98	58.41	38.98

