90	98.08	92.68	87.66	80.86	72.41	62.72	42.16

With a planned sample size of 600 per arm and 15% attrition, if the observed rate of infection in the Pfizer 2023-2024 formulation arm differs from 60 per 100,000 person-days, 600 participants in each arm assures 80% power to claim non-inferiority for observed rVE greater than 10, sometimes less than 10, as outlined in the table above. The grey cells in the table indicate which scenarios will have 80% power with 600 participants.

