# 4. SAMPLE SIZE AND POWER CONSIDERATIONS

# 4.1 Sample Size for Primary Objectives

Power and sample size are examined for both primary objectives to 1) compare VE between vaccinated arms (both NVX and mRNA) and the non-vaccinated comparison arm with a 2-sided alpha=0.05 superiority test and 2) determine non-inferiority of NVX 2023-2024 formula vaccine variant compared to a single dose of Pfizer mRNA 2023-2024 updated vaccine with a 1-sided alpha=0.05

confidence interval. The rate of CLI-associated SARS-CoV-2 infection, confirmed by COVID-19 rapid antigen test (RAT) in those not vaccinated with the 2023-2024 formulation is expected to be 80 per 100,000 person-days. We expect those choosing not to vaccinate in Fall 2023 to Spring 2024 to be a mix of unvaccinated and fully vaccinated but not boosted individuals, but to be conservative we will assume this group is solely comprised of fully vaccinated individuals. Using publicly available data on the historic case rates in Utah for COVID-19 from the week of October 2, 2022 to the week of May 21, 2023 [CITE https://coronavirus-dashboard.utah.gov/risk.html], the average rate of cases in those fully vaccinated in Fall 2022-Spring 2023 is 56.63 per 100,000 person-days for those fully vaccinated. From a survey conducted in spring of 2022, it has previously been reported that of those testing for COVID-19 44.2% report testing at a lab or clinic and 25.7% reported testing at a drive-thru clinic. Therefore, using at-home test kits to identify cases, we expect rates to be 43.1% higher (1/(0.257+0.442)) than what is shown on Utah's dashboard. This under-reporting adjustment to Utah's observed rates from last fall leads to a conservative estimate for the rate of CLI-associated SARS-CoV-2 infection, confirmed by COVID-19 rapid antigen test (RAT), in those not vaccinated with the 2023-2024 formulation to be 80 per 100,000 person-days. Using the same logic applied to the reports for those with a bivalent booster last fall, after adjusting for under-reporting, we estimate the infection rate to be 68 per 100,000 person-days in those vaccinated in Fall 2023 to Spring 2024.

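### The 81.12% non-inferiority power assumes 60 per 100,000 person-days in the Pfizer arm, but the protocol plans 48 for the vaccinated; there power is about 73% at rVE 10 and 58% at rVE 0, and the general 80% assurance fails at rate 50

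*Protocol*

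**What the plan says.** Protocol section 6.1.1 gives two planning rates. The rate "in those not vaccinated with the 2023-2024 formulation is expected to be 60 per 100,000 person-days". For the other group, "we estimate the infection rate to be 48 per 100,000 person-days in those vaccinated in Fall 2023 to Spring 2024".

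For the second primary objective, the same section sets a margin of rVE -50 (hazard ratio 1.5) and tests it "with a 1-sided alpha=0.05 confidence interval". It plans 600 per arm with 15% attrition, and summarises: "If we assume an infection rate of 60 per 100,000 person-days in the Pfizer vaccinated arm we have 81.12% power to determine non-inferiority", for an rVE of at least 10. Table 5 gives power for Pfizer-arm rates of 50, 60, 70, 80 and 90. The text after the table considers a Pfizer rate other than 60 and says that "600 participants in each arm assures 80% power to claim non-inferiority for observed rVE greater than 10", and sometimes below 10.

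SAP section 4.1 repeats the 81.12% sentence, the same table (its Table 2) and the same assurance, but under different planning rates. There the rate "in those not vaccinated with the 2023-2024 formulation is expected to be 80 per 100,000 person-days", and for the vaccinated "we estimate the infection rate to be 68 per 100,000 person-days in those vaccinated in Fall 2023 to Spring 2024". Protocol section 6 says of the analysis plans: "These plans have been updated to reflect revised power calculations based on more accurate estimations of assumed rates of infection".

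**The concern.** The rate used for the Pfizer arm in the power statement equals the protocol's planning rate for people who are not vaccinated. No reason is given. The protocol's own estimate for the vaccinated, 48, lies below the lowest row of Table 5, so a reader cannot look up the power under the stated plan. Fewer infections mean less power, so the choice flatters the figure.

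The two documents suggest how this arose. Against the SAP's vaccinated rate of 68, a Pfizer rate of 60 is cautious. Against the protocol's 48, the same 60 is optimistic, yet the non-inferiority text and table are identical in both.

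Non-inferiority of NVX is a primary objective. A reader who takes the chance of success to be 81% will read a failed non-inferiority result as stronger evidence against NVX than it would be. The general assurance after Table 5 adds to this, because it presents 80% power as holding whatever the Pfizer rate.

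**Working it through.** **Inputs (Protocol section 6.1.1).** 600 per arm less 15% gives 510. The margin is a hazard ratio of 1.5, with one-sided alpha 0.05 (z = 1.645). Follow-up is 24 weeks, or 168 days. Event probability is rate × 168, which is how the protocol gets 10.08% from 60. The hazard ratio is HR = 1 − rVE/100. The rVE values in the table are treated as the assumed true values.

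**Formula.**
- Pfizer probability: pC = rate × 168 / 100,000
- NVX probability: pT = 1 − (1 − pC)^HR
- Events: D = 510 × (pC + pT)
- Power = Φ( √(D/4) × ln(1.5/HR) − 1.645 )

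**Reproducing the plan's figure (rate 60, rVE 10).** pC = 0.1008 and pT = 1 − 0.8992^0.9 = 0.0912, so D = 510 × 0.1920 = 97.9. Then √(97.9/4) = 4.948 and ln(1.5/0.9) = 0.5108. Power = Φ(2.527 − 1.645) = 81.13%, against 81.12% stated. The formula reproduces all 35 cells of Table 5 to within 0.02 points.

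**At the protocol's vaccinated rate of 48.** pC = 0.08064.
- rVE 0: D = 510 × 0.16128 = 82.3; power = Φ(4.535 × 0.4055 − 1.645) = 57.7%.
- rVE 10: pT = 0.0729, D = 78.3; power = Φ(4.424 × 0.5108 − 1.645) = 73.1%.

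The missing row, beside the two nearest printed rows (power, %):

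| Pfizer rate | rVE 20 | 10 | 5 | 0 | -5 | -10 | -20 |
|---|---|---|---|---|---|---|---|
| 48 (computed) | 85.6 | 73.1 | 65.6 | 57.7 | 49.7 | 41.9 | 27.9 |
| 50 (Table 5) | 86.88 | 74.60 | 67.13 | 59.16 | 51.02 | 43.03 | 28.63 |
| 60 (Table 5) | 91.71 | 81.12 | 74.00 | 65.94 | 57.33 | 48.57 | 32.20 |

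Solving for 80% power: at rVE 10 the Pfizer rate must be at least about 58.1; at rate 48 the rVE must be at least about 15.1.

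**The assurance, tested at rate 50.** Power is 74.6% at rVE 10, 76.0% at 11, 77.4% at 12, 78.7% at 13 and 80.0% at 14. The statement is therefore untrue for rVE between 10 and about 14. Table 5's own 74.60% at rVE 10 already shows that power just above 10 cannot be 80%.

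**At the SAP's vaccinated rate of 68.** Power is 70.7% at rVE 0 and 85.2% at rVE 10.

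**The case against.** The best defence is that nothing is miscalculated. The 81.12% is conditional, naming both the rate of 60 and the rVE of 10. Table 5 follows directly, and its row for 50 is only about 1.5 points above the row for 48 at rVE 0 and rVE 10. Most of the fall from 81.12% to 57.7% comes from the assumed effect: the change of rate takes 8.0 points (81.12 to 73.1 at rVE 10), and moving from rVE 10 to 0 takes the other 15.4. At rate 60 an equivalent NVX would already miss the criterion 34% of the time (100 − 65.94). All of this is right, and it limits the point to the rate used and the wording. It does not explain why a vaccinated arm carries the unvaccinated rate.

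The assurance refers to the table, and the next sentence says that grey cells mark the scenarios with 80% power. At the only tabulated rVE above 10, namely 20, every row exceeds 80%. The shortfall at rate 50 is at most 5.4 points, and at rates of 60 and above the assurance holds. But shading can mark only tabulated cells, while the sentence makes a general claim that the row for 50 contradicts.

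Two further points have some force. First, 48 implies a VE of 20% against 60 (1 − 48/60), whereas the case counts in the same section assume a VE of 50%, which would put the vaccinated at 30. Power there would be lower still: about 42% at rVE 0 and 56% at rVE 10. Second, the SAP is dated October 11, 2023 and may predate the protocol's revised rates. That could explain the conflict, but the protocol says the plans were updated, so the rates still need to be reconciled.

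**Conclusion.** The concern holds. The 81.12% is correct for a Pfizer rate of 60 and rVE 10, but it is not the power under the protocol's own plan. At the planned vaccinated rate of 48, power is about 73% at rVE 10 and 58% at rVE 0, so a truly equivalent NVX would fail the non-inferiority criterion about 42% of the time. The assurance of 80% power for rVE above 10 is untrue at rate 50 for rVE between 10 and about 14. In the SAP the 81.12% is cautious relative to its own rate of 68, but the assurance has the same fault, and the planning rates disagree with the protocol's.

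These figures rest on the plan's own margin, alpha, attrition and conversion of rates to probabilities. The fault lies in the stated power. The sample size is based on the first primary objective and is not affected. This should be fixed, but it does not undermine the design.

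**What to change.** In Protocol section 6.1.1:
- Restate the non-inferiority power at 48 per 100,000 person-days (about 58% at rVE 0 and 73% at rVE 10), or justify 60 for the Pfizer arm.
- Add the row for 48 to Table 5.
- Replace the assurance after the table with a statement of which combinations of rate and rVE reach 80%, or delete it.

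In SAP section 4.1:
- First reconcile the planning rates (80 and 68) with the protocol's (60 and 48).
- Then state power at the agreed vaccinated rate; if 68 is kept, this is about 71% at rVE 0 and 85% at rVE 10.
- Make the same correction to the assurance after Table 2.

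The cost is wording and one table row, and the stated power becomes less favourable. Sample size, margin, endpoint and decision rule stay as they are.

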6.2 Statistical Analysis

The modified intent-to-treat (mITT) population will be the primary population for efficacy analyses and participants are analyzed according to their randomized treatment. All participants who are randomized, received a study vaccine, and participated in study surveillance by responding to at least one surveillance contact during the SARS-CoV-2 circulation period (active surveillance) will be included in the mITT population for the primary objectives. For participants who were identified as not receiving a 2023-2024 updated vaccine (comparison group) they will be analyzed in that group under the mITT population, even if they subsequently do get a 2023-2024 updated vaccine from elsewhere during the study period.

Additionally, a per protocol analysis will also be performed. The per protocol population will include participants who met eligibility criteria, received study vaccine per protocol, participated in study surveillance by responding to at least one surveillance contact during the SARS-CoV-2 circulation period (active surveillance), and did not receive another SARS-CoV-2 vaccine outside of the study during the study period. If participants were in the non-vaccinated comparison group but subsequently received a 2023-2024 updated vaccine, they will be censored at that point.

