5.5.3.2 Vaccination Reporting

Influenza vaccination status will be reported by the participants (including type of vaccine, location, and date of vaccination) through the Mid-Study and End-of-Study (Appendix O) Surveys. Receipt of 2023-2024 updated COVID-19 vaccine outside of the study during the study period will similarly be self-reported through the Mid-Study and End-of-Study Surveys. Should a participant in the non-vaccinated arm of the study receive an updated COVID-19 vaccine during the study period, that information will be captured via the Mid-Study Survey & End-of-Study Surveys (Appendix O), or the Vaccine Abstraction Verifications (Appendix N1-N2) but the participant will remain in the study. Participants will also be asked to provide their COVID-19 and influenza vaccination history through self-report and the upload of vaccine documentation to their participant dashboard. Examples of documentation include a digital photo of the vaccination receipt or immunization records. These documents can be uploaded only via the participant dashboard.

In addition to the responses provided in the eligibility and enrollment surveys, previous COVID-19 vaccination data will be retrieved through USIIS by study staff or provided by the participant (vaccine card or immunization records) to determine eligibility. The study team will collect the vaccine manufacturer information. This information is important due to the exclusion criteria centered around receipt of the J&J vaccine. There were a small proportion of Utah residents who received the J&J Vaccine (<8%, 166581/2082443). The vaccine type, other than J&J, will represent what is commonly done in pragmatic study designs. The study team will track the prior vaccination manufacturer to see if there may be interactions between different combinations of vaccines. From a clinical perspective there is no concern with a heterologous vaccination approach, as there have been a number of studies which demonstrate that such an approach is clinically appropriate. This has led to the CDC issuing guidance supporting "mix-and-match" vaccine strategy.

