For the superiority test of the first primary objective, on which the sample size is based, the null hypothesis that vaccine efficacy, or VE, of the 2023-2024 formula compared to no vaccination in Fall 2023-Spring 2024 is 0 is tested against the alternative that the VE is not equal to 0. That is, H_0 : VE = 0 is tested against H_a: VE ≠ 0. VE is calculated as 1- hazard ratio, HR, comparing those receiving the 2023-2024 formulation (either NVX or Pfizer) to those choosing not to be vaccinated in Fall 23 to Spring 24, times 100 or 100*(1-HR). HR will be estimated using Cox proportional hazards models with α =0.05. Table 4 provides the required sample size to yield 80% power to detect VE of 40%, 50%, and 60% or higher, assuming an attrition rate of 15% or less. We plan that the NVX and Pfizer arms will each have twice as many participants as the arm of those choosing no Fall 2023 to Spring 2024 vaccination, a ratio of 4:1. Calculations were made in PASS using the Multi-Arm Tests for Treatment and Control Survival Curves using Cox's Proportional Hazards Model⁴¹. In 24 weeks of follow-up, the rate of 60 cases per 100,000 person-days equates to an event probability of 10.08%. This probability corresponds to a hazard rate of 0.10625. With a total of 1500 participants enrolled (1200 with 2023-2024 formulation and 300 without Fall 2023 to Spring 2024 vaccination), we have 80% power to detect a VE of 56.25% or more, even if we see 15% attrition. With 1500 enrolled and an observed VE of 50%, we anticipate there will be approximately 85 RAT confirmed symptomatic COVID-19 cases in total (30 in the not vaccinated arm and 55 in the vaccinated arm) with no attrition, and 72 with 15% attrition.

Table 4. Relationship between Vaccine Efficacy and Sample Size, assuming a 4:1 ratio vaccinated						
with 2023-2024 formulation to not vaccinated in Fall 2023-Spring 2024 and 15% rate of attrition.						
Lowest Detectable VE comparing between non-vaccinated and Sample size for 80% power						
vaccinated (NVX and Pfizer combined) arms						
40%	3,183					
50%	1,954					
56.25%	1,500					
60%	1,289					

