#### 6. ANALYSIS POPULATIONS

#### **6.1 Modified Intent-to-Treat Population**

All participants who are randomized, received a study vaccine, and participated in study surveillance by responding to at least one surveillance contact during the SARS-CoV-2 circulation period (active surveillance) will be included in the modified intent-to-treat (mITT) population for the primary objectives. The mITT population will be the primary population for efficacy analyses and participants are analyzed according to their randomized treatment. For participants who were identified as not receiving a booster

(comparison group) they will be analyzed in that group under the mITT population, even if they subsequently do get a vaccine during the study period.

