#### **6.2 Per Protocol Population**

The per protocol population will include participants who met eligibility criteria, received study vaccine per protocol, participated in study surveillance by responding to at least one surveillance contact during the SARS-CoV-2 circulation period (active surveillance), and did not receive another SARS-CoV-2 vaccine outside of the study during the study period. If participants were in the non-vaccinated comparison group but subsequently received a vaccination, they will be censored at that point.

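### The primary VE analysis counts decliners' time after an outside 2023-2024 dose as comparison-group time, although the hypothesis is stated against no vaccination

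*Protocol*

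**What the plan says.** Protocol 6.2 makes mITT the primary efficacy population. Of comparison participants (Arm 3) it says "they will be analyzed in that group under the mITT population, even if they subsequently do get a 2023-2024 updated vaccine from elsewhere". SAP 6.1 repeats the rule: "they will be analyzed in that group under the mITT population, even" if they are vaccinated later in the study.

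The contrast for Objective 1 is described in two ways:

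- **Against no vaccination.** Protocol 6.1.1 gives the null as VE "of the 2023-2024 formula compared to no vaccination in Fall 2023-Spring 2024 is 0 is tested" against a two-sided alternative, and SAP 4.1 does the same. The Protocol's opening summary places in this group people who decide against vaccination for the study period.
- **Against declining.** Protocol 4.1 and SAP 1.1 word the objective as a comparison with people who are recommended the updated vaccine and decline it. Protocol 6.1.2 and SAP 8.3.1 use similar language.

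Outside doses are provided for. Protocol 5.5.3.2 begins "Should a participant in the non-vaccinated arm of the study receive an updated COVID-19 vaccine during the study period" and goes on to say that the dose is captured by the mid-study and end-of-study surveys or by vaccine record abstraction, and that the person stays in the study. The per-protocol rule in SAP 6.2 is different from the mITT rule: "If participants were in the non-vaccinated comparison group but subsequently received a vaccination, they will be censored at that point". SAP 8.3.3 lists the per-protocol analysis as a sensitivity analysis.

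**The concern.** A decliner who gets the same formula elsewhere is, from then on, a vaccinated person whose time at risk counts as comparison time. Set against a hypothesis of vaccine versus no vaccine, that is misclassified exposure in the primary analysis.

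The usual reason for analysing people as assigned is to preserve randomisation. That reason is absent here: participants choose whether to be in Arm 3 (opening summary; Protocol 5.5.3, Blinding). The randomised NVX versus mRNA comparison is a separate objective and is not affected.

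Two things are at stake. The headline VE could be diluted by a component that the planned data would allow the sponsor to remove. The power statement in Protocol 6.1.1 allows for 15% attrition but not for crossover.

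**Working it through.** **Inputs from Protocol 6.1.1**
- The test compares vaccinated participants with "the non-vaccinated comparison arm with a 2-sided alpha=0.05 superiority test".
- Over 24 weeks, "the rate of 60 cases per 100,000 person-days equates to an event probability of 10.08" per cent. "This probability corresponds to a hazard rate of 0.10625", which checks: -ln(1 - 0.1008) = 0.10625.
- 1,200 vaccinated and 300 not, with 15% attrition, leaves 1,020 and 255.
- Stated result: 80% power at VE 56.25% (HR 0.4375).

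**Reproducing the stated power**
- Events = 1,020 × (1 - exp(-0.10625 × 0.4375)) + 255 × (1 - exp(-0.10625)) = 46.3 + 25.7 = 72.0.
- Schoenfeld: z = √(72.0 × 0.8 × 0.2) × |ln 0.4375| - 1.96 = 3.395 × 0.8267 - 1.96 = 0.847, so power is 80.1%. This matches the plan.

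**Adding crossover**

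Let f be the share of Arm 3 person-time that follows an outside dose. The documents give no value, so f is an assumed range. I also assume that the outside dose works at once and as well as the study dose. That assumption gives the most dilution for a given f.

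- *Current mITT rule:* the average Arm 3 hazard is multiplied by (1 - f × VE), so apparent HR = (1 - VE)/(1 - f × VE). Example at f = 10%: 0.4375/(1 - 0.05625) = 0.4636, an apparent VE of 53.6%. Events are 70.7 and power is 73.4%.
- *Censoring at the outside dose:* HR stays at 0.4375 if censoring is non-informative, but Arm 3 loses the share f of its person-time. Example at f = 10%: events = 46.3 + 255 × 0.9 × 0.1008 = 69.5; vaccinated share = 1,020/(1,020 + 229.5) = 0.816; power is 76.1%.

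| f | Apparent VE, mITT | Power, mITT | VE, censored | Power, censored |
|---|---|---|---|---|
| 0 | 56.25% | 80.1% | 56.25% | 80.1% |
| 5% | 55.0% | 76.9% | 56.25% | 78.2% |
| 10% | 53.6% | 73.4% | 56.25% | 76.1% |
| 20% | 50.7% | 65.4% | 56.25% | 71.2% |

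**What f means in people**

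If outside doses were spread evenly over the first 84 of the 168 days, each crossover would contribute on average (168 - 42)/168 = 75% of their time after the dose. Then f = 5%, 10% and 20% correspond to about 7%, 13% and 27% of decliners crossing over.

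**Cross-check by simulation**

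The same design was simulated with that timing and a Wald test on the log rate ratio. Power was higher throughout (87.6% with no crossover), but the ordering was the same. With 10% of decliners crossing over, power was 83.4% under mITT and 85.6% with censoring; with 20%, 77.6% and 83.3%. The Schoenfeld figures are the ones comparable with the plan's 80%.

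**The case against.** The strongest reply is that the rule is a deliberate treatment-policy choice. The objective is worded in terms of declining, and analysing decliners as decliners fits that wording. This stands in part. A reader might infer that the primary analysis fails to address its own objective; the documents do not support that, because the conflict is with the hypothesis and the definition of the comparison group. No estimand is declared, so the texts need reconciling on either reading.

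A reader might also infer that the plan ignores crossover. It does not: the per-protocol analysis already censors at the outside dose. However, that analysis is secondary. It also restricts on eligibility and removes vaccinated participants who had an outside dose, so a difference between it and mITT could not be put down to crossover alone.

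The size is also open to challenge, and rightly. The text on outside vaccination is conditional and no rate is given. Arm 3 consists of people who have decided against vaccination, and Protocol 5.5.3 lets those who change their minds at enrollment join the vaccinated arm if space remains. Crossover may be low.

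Finally, censoring has costs. It may be informative if people seek an outside dose because of perceived risk or health, it takes person-time from the smallest arm, and it recovers only part of the lost power.

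**Conclusion.** The concern holds in a limited form. The primary mITT rule conflicts with the Objective 1 hypothesis, and there is no randomisation in that comparison for the rule to protect.

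At a true VE of 56.25%, the loss runs from 1.3 VE points and about 3 points of power at f = 5% to 5.6 VE points and about 15 points of power at f = 20%. These figures rest on an assumed f, an equally and immediately effective outside dose, and an average-hazard approximation. Near f = 0 the issue is one of wording.

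It is tempting to conclude that the reported VE will be biased downward overall. The documents do not support that. Only the crossover component has a known direction, and only if the vaccine works. Arm 3 is self-selected, so confounding could move VE either way. Nor do the documents show that the trial will miss its power target through crossover, since they give no rate. What can be said is that the stated 80% leaves no room for it.

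**What to change.** For Objective 1 only, amend Protocol 6.2 and SAP 6.1 and 8.3.1:

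- In the primary VE Cox analysis, censor an Arm 3 participant at the date of any outside 2023-2024 dose, taken from the surveys and record abstraction. Keep every other mITT rule unchanged, so that the effect of this one rule can be isolated.
- Report the current as-declined analysis as a named sensitivity analysis.
- Align the objective (Protocol 4.1, SAP 1.1) and the hypothesis (Protocol 6.1.1, SAP 4.1) to that one contrast.
- Leave the randomised rVE analysis by assigned vaccine.

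The cost is wording plus one data step. Outside-dose capture, the counting-process Cox model and a censoring rule are already planned. The change should be settled before unblinding. The remaining weaknesses are lost Arm 3 person-time, possibly informative censoring, and imperfect dose dates: the surveys are only mid-study and end-of-study, so some dates rest on recall, and participants may opt out of the registry query (Protocol 5.5.3.1). The retained sensitivity analysis shows how much the choice of rule matters.
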